This adaptive study design employs the possibility of subsequent randomizations if pre-designated targets are not reached. All participants will be ages 2-6 years old and in the continuation phase of the Medtronic CEP 302 Trial using the Medtronic MiniMed 670G pump with Guardian 3 sensor. All subjects will receive the same standardized education on using the pump with hybrid closed loop capabilities and continuous glucose monitoring (CGM) during the initial Medtronic CEP 302 trial phase. A review session will also take place as they enter the extension phase of the study which is the beginning of this study. Their uploaded data will be reviewed every two weeks and if they are not meeting adherence ($\geq 70\%$ of the time in closed-loop) and glycemic target goals ($\geq 65\%$ of sensor values between 70 - 180 mg/dL), they will be randomized to six interventions: 1) reduce psychological distress, 2) reduce worries about hypoglycemia, 3) education and understanding of developmental and technologic demands for using hybrid closed loop this age group, 4) understanding and modification of carbohydrate to insulin ratios, set point and in depth nutritional education, and interventions 5) and 6) will be minimal interventions with a text message providing information on how they are doing at meeting their targets. All these interventions will be compared to a minimal intervention (text of their results compared to target goals). We will examine group differences over a 3-month period on health and psychological outcomes at baseline and after three months.

Objectives: The objective of this study is to assess several remote interventions with families in the extension phase of the 670G toddler study to determine which interventions are most effective in improving their time in target (70-180 mg/dl) and their adherence in maintaining closed-loop control (at least 70% of the time in closed-loop).

Sample Size:

- We anticipate enrolling at least 4 subjects at each of the current sites, and would like to expand the number of sites to include Yale, and the University of South Florida. Each of these sites is scheduled to enroll at least 4 toddlers, and some will enroll up to 8. We therefore anticipate being able to enroll at least 30 subjects. A sample size of 26 subjects should allow for a statistically significant result with a power of 0.9 and a p of 0.05. Enrollment of 30 subjects would allow for a 10% drop out rate. See Biostatistics and Data Analysis section.

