The study design is adaptive, specifically a SMART (sequential multiple assignment randomization trial). A SMART is an adaptive study design that allows for multiple assessments and based on the results of those assessments, a menu of interventions can be deployed. To ensure that there is no bias when interventions are delivered, and to have a test of whether those who receive the intervention fare better (or worse) from those who do not receive the intervention, a randomization strategy is used. The decision to use a SMART was primarily made because this is what happens clinically – a child (and family) start on a system with a certain dose of education and when problems arise, the clinical team offers interventions to optimize their use of the system. The SMART allows us to test which interventions are best for this patient population that presents many unique challenges for diabetes management and coordinated care from the team.

All participants will complete a *checkpoint* visit every 2 weeks for the duration of 3 months. At each checkpoint in the study (weeks 2, 4, 6, 8, and 10), data from the preceding 2 weeks will be reviewed to determine if there have been “failures.” Data will be available through pump uploads and by asking caregiver participants the frequency of wearing the devices. Objective data will guide determination of failures. We are defining failure in the following ways:

- 1) Adherence Failure: defined as using the hybrid closed loop “Auto Mode” less than 70% during a week
- 2) Glucose Failure: defined as less than 65% time spent in glucose range of 70 - 180 mg/dL.

If subjects pass both the adherence and glucose targets, no intervention is required. If there is an Adherence Failure, they will be eligible for an adherence intervention. The adherence interventions

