will be randomized by order and the sequence of interventions will depend on whether a previous intervention has been administered. The participant may receive a minimum of zero adherence interventions over the 3 month period to a maximum of 5 adherence interventions during the 3 month period. A similar sequence of interventions will occur if patients experience a Glucose Failure. Finally, if subjects have both an Adherence Failure and a Glucose Failure at a checkpoint, they will enter the adherence intervention pathway. They will continue on this path until they have completed all three possible interventions. After this time, if they continue to failure both adherence and glucose targets, they will enter the glucose target intervention pathway. We decided that an adherence failure trumps a glucose failure because using the Auto Mode function is critical to opening the door to achieving glucose targets.

The figure below shows the possibilities at each 2-week checkpoint.

Figure 1. Potential interventions at 2 week monthly visit

[figure not shown]

Figure 1 above graphically depicts the treatment scheme for participants in the SMART. Below, the conditions and possible scenarios are described in more detail. As a reminder, there are five checkpoints (2, 4, 6, 8, and 10 weeks). At each checkpoint, here are the possible scenarios. A = adherence; G = glucose range; and R = randomization below:

1. If 1st A failure, R to A1, A2, or A3
2. If 2nd A failure (ie., there was a previous A failure), and a history of A3, R to A1 or A2
3. If 2nd A failure, with history of (respectively) A1(A2) give A2(A1).
4. If A success, 1st G failure, R to G1,G2,G3
5. If A success, 2nd G failure, w/ history of G3, R to G1,G2
6. If A success, 2nd G failure, w/history of (respectively) G1(G2) give G2(G1).
7. All else, no treatment.

As noted above, an Adherence Failure is defined as use of Auto Mode for less than 70% of the time at a checkpoint. A Glucose Failure is defined as spending less than 65% of the time in the 70 - 180 mg/dL range at a checkpoint. Also note that the final visit at 3 months is the end of the study and no interventions are offered at that study visit.

Study Group

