| Satisfaction with Glucose Monitoring | The Glucose Monitoring System Satisfaction Survey (GMSS-T1D) is a validated tool used to assess treatment satisfaction with glucose monitoring devices and its impact on quality of life and other patient-reported outcomes. | 15 items. 5-10 minutes to complete. |

| | | |
|---------------------------------|--|--|
| Use and Comfort with Technology | Objective questions documenting the frequency of use and types of technologies used. Both general (e.g., smartphone) and diabetes-specific (e.g., trend program). | 23 items. 5 minutes to complete. |
| Demographic and Family Data | Parents will complete a questionnaire on the family's structure, racial and ethnic background, indicators of socioeconomic status, insurance status (public vs. private), and other essential characteristics. | 5 minutes |
| Behavioral Outcomes | | |
| Diabetes management behaviors | Amount of time spent in Auto Mode; blood glucose monitoring frequency (by meter download); adherence to pump boluses; | Download (no time burden for participants) |
| Health care utilization | Number of visits and calls to the diabetes care team | Tracking by interview (10 minutes to complete) |

Table 4. Measures obtained from child

| | | |
|-----------------------------|--|---|
| Health Outcomes | | |
| HbA1c measurement | Participants will provide a small fingerstick sample of blood (capillary) during their routine clinic visit. This will be done using the DCA in clinic or local lab method. | Gold standard measure of glycemic control |
| Glycemic excursion measures | Time in range (70 to 180 mg/dL); percent below 70 and 60 mg/dL as indicators of hypoglycemia, and above 180 and 250 mg/dL as indicators of hyperglycemia; additional indices of variability including standard deviation will also be calculated | |

In addition, parents will be asked to complete a brief online survey (< 10 minutes) at the following intervals since randomization – 4, 8, and 12 weeks. These online surveys will consist of the Diabetes Distress Scale (3 items), PHQ-8 (8 items), and the short form of the STAI (10 items). All surveys can be completed online via RedCap.

Schedule

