The primary effect we are interested in is percent change in the amount of time spent in the target glucose range from baseline to study completion. Data from our CGM study with toddlers (NIDDK funded DP3; [name] PI) show that of the sixteen 2-6 year-olds in the study they achieve, on average, only 45% time in 70-180 mg/dL target range (standard deviation = 15%). Our hypothesized change will be a 10% improvement in time spent in target range. There is sufficient power (0.9) to detect this change in a sample size of 26. Another aspect of calculating power in this study is the actual number of participants exposed to the planned interventions after a glucose “failure.” Over 90% of the participants in our DP3 toddler study experienced a glucose failure of less than 60% time in target range. Further, the table below shows the results of glucose failures from the DirectNet cohort of toddlers using CGM (Ped Diabetes 13:301-7, 2012).

Table 1. Expected Failure Rates

| | Months | | | | | | |
|---|--------|-----|-----|-----|-----|-----|-----|
| | 0 | 1 | 2 | 3 | 4 | 5 | 6 |
| Glucose Failure (not having at least 65% of readings in the 70-180 mg/dL range) | - | 70% | 70% | 70% | 70% | 75% | 75% |

The SMART design of our proposed study allows for randomization to one of 3 conditions when there is a glucose failure (2 interventions and 1 control). Because of this, participants can contribute to more than one comparison which increases power. This makes the SMART design very efficient, particularly when examining multiple treatment strategies, which is what clinicians do in these cases. Our primary outcome will be Glucose Failure, which we expect 80-90% of participants to experience. With 27 participants available for randomization after a Glucose Failure and each subject assigned at least once to each of the three intervention groups, there is only 73% power to detect a difference of 10% change in time spent in range for a given intervention. In other words, going from 45% time spent in range at baseline to 55% time spent in range at study completion; an outcome of 10% change. Thus, while the percent change in the sample from baseline to the end of the continuation phase does appear to be adequately powered for the group, the testing of individual interventions is underpowered. We will proceed with caution when estimating likely effect sizes for each intervention based on the results of the planned analyses.

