Our primary outcome will be tested in two ways. First, by using latent growth curve models to compare change in response to treatment strategies, we can examine outcomes from checkpoint to checkpoint. For example, we can test percent change in time spent in range from week 2 to 4 and determine which intervention is associated with promotion of change during that time period. Because more than three time points are available in this study, nonlinear trajectories will also be examined. Second, we will also examine the treatment effect using separate individual trajectory models for the primary outcome across the entire 3 months of the study. These analyses will inform more precise sample size considerations based on observed effect sizes for a larger efficacy trial conducted after this proposed research is completed.

Study population

The patient population is children with type 1 diabetes and their parents who are actively enrolled in the IRB and FDA approved Medtronic CEP302 study (IDE# G150247, NCT02660827) . Parents (18 years and older) will provide informed consent for their own participation and parental permission for their child to participate. We will enroll and randomize 40 families.

Eligibility criteria

To be eligible for the study, a child must meet the following criteria:

1. Enrollment in the continuation phase of the Medtronic CEP 302 study
Ages 2 to <7.0 years of age

Expected duration of the study participation

Duration of study participation is expected to be three months.

Start Date: As early as September, 2017.

End Date: As late as September, 2018

Adverse Event Reporting and Safety Monitoring

Overview of Safety Monitoring

All participants will have glucose data reviewed at planned intervals for study adherence. All of the other medical monitoring of these subjects are done as part of the IRB and FDA approved Medtronic CEP302 study (IDE# G150247, NCT02660827)

Definition of Adverse Event

Adverse event reporting and definitions for these research participants will be defined and carried out via the IRB and FDA approved Medtronic CEP302 study (IDE# G150247, NCT02660827), as these encompass all the inherent risks of Type 1 Diabetes, insulin pump use, and continuous glucose sensor use.

Recording of adverse events

Reportable adverse events and serious adverse events are defined and carried out in accordance with the IRB and FDA approved Medtronic CEP302 study (IDE# G150247, NCT02660827)

Data and safety monitoring

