There will be no cost to the subjects to participate in this research study. Parents will receive \$50 for each of two surveys, completed at the enrollment and final visits. In total, a family can receive \$100 for completion of the study.

Subject withdrawal

Participation in the study is voluntary, and a subject may withdraw at any time. The investigator may withdraw a subject who is not complying with the protocol. For subjects who withdraw, their data will be used up until the time of withdrawal.

Confidentiality

For security and confidentiality purposes, subjects will be assigned an identifier that will be used instead of their name. De-identified subject information may also be provided to research sites involved in the study.

Level of risk

This research proposal in children is consistent with 21 CFR 50.51 - Clinical investigations involving not involving greater than minimal risk

Devices

There are no study devices other than those used in the IRB and FDA approved Medtronic CEP302 study (IDE# G150247, NCT02660827)

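### Investigator withdrawal for undefined non-compliance cuts off a family's data in a trial of adherence, so loss of the week-12 value can be related to outcome

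*Combined protocol and SAP*

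**What the plan says.** Under Subject withdrawal the protocol states: "The investigator may withdraw a subject who is not complying with the protocol". It goes on: "For subjects who withdraw, their data will be used up until the time of withdrawal". It does not say what counts as not complying, and it plans no collection of data after withdrawal. If the second sentence covers only families who leave of their own accord, the handling of families removed by the investigator is not stated at all.

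Adherence has three other roles in the plan.

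- **Trigger.** In Study Procedures, "an Adherence Failure is defined as use of Auto Mode for less than 70% of the time at a checkpoint". The consequence is an intervention: "If there is an Adherence Failure, they will be eligible for an adherence intervention".
- **Objective.** The Objectives paragraph of the synopsis names adherence to closed-loop use, at the same 70% threshold, beside time in target.
- **Outcome.** Table 3 lists, under Behavioral Outcomes, "Amount of time spent in Auto Mode; blood glucose monitoring frequency (by meter download); adherence to pump boluses".

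The primary effect in Biostatistics and Data Analysis is the "percent change in the amount of time spent in the target glucose range from baseline to study completion". It is to be tested first "by using latent growth curve models to compare change in response to treatment strategies" and second with individual trajectory models over the three months. No analysis population, missing-data assumption or sensitivity analysis is given.

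**The concern.** A withdrawal rule based on non-compliance is harmless when compliance has little to do with the outcome. Here the two are close. Study Procedures puts adherence failure ahead of glucose failure because Auto Mode use is held to be critical for reaching the glucose targets. A family that struggles with the system or the sessions is thus more likely than average to have a poor time-in-range result. If such a family is removed, its later checkpoints and its week-12 value are lost, and that loss is related to what those values would have been.

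The decision is also taken after randomisation, at the site's discretion, on a term that the protocol leaves open. The Overview of Safety Monitoring adds to the looseness by saying that glucose data are reviewed for study adherence, which blurs compliance with the protocol and adherence to the device. At stake are the baseline-to-completion change and the per-intervention effect sizes. The plan intends to use observed effect sizes to size a larger efficacy trial.

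**Working it through.** **1. The plan's own figure.** Inputs from the synopsis and Biostatistics and Data Analysis: change of 10 points (45% to 55%), SD 15, p of 0.05, power 0.9, 26 subjects, 30 enrolled to allow 10% dropout. A one-sample t-test on change, two-sided, with 15 taken as the SD of change, needs n = 26 (power 0.904). The figure reproduces. With 10% lost, 30 × 0.9 = 27 remain, with power 0.915. The allowance therefore protects power. It does nothing about which families are lost.

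**2. Shift in a completers-only mean.** Let k of N families be withdrawn, and let D be the mean change of completers minus the mean change that the withdrawn families would have shown.

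shift = completer mean − full mean = (k/N) × D

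Assume that completers gain 10 points and withdrawn families gain 0, so D = 10:

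- k = 3, N = 30: full mean = 10 × 27/30 = 9.0, shift 1.0.
- k = 6, N = 30: full mean = 10 × 24/30 = 8.0, shift 2.0.

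Neither D nor k comes from the documents. Only 3 of 30 matches a planned number, and that allowance is for dropout of any cause.

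**3. Sensitivity to the mechanism.** Simulation with 4,000 runs per scenario, change Normal with SD 15, N = 30, analysing only children with a week-12 value. The percentages are the chance of declaring improvement when there is none (nominal upper tail 2.5%).

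| Withdrawn | Correlated about 0.7 with poor change | Exactly the worst removed |
|---|---|---|
| 2 of 30 | 1.4 points, 8% | 2.0 points, 13% |
| 3 of 30 | 2.0 points, 13% | 2.8 points, 22% |
| 6 of 30 | 3.6 points, 25% | 5.1 points, 53% |

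Withdrawal unrelated to outcome gives no bias (within 0.15 points). By the formula in step 2, the 3-of-30 row needs D = 2.0/0.1 = 20 to 2.8/0.1 = 28 points, or 1.3 to 1.9 SD. These are strong mechanisms, and they mark an outer range for an endpoint-only analysis. They are not an estimate for this plan.

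**4. Between interventions.** For an active arm A against the minimal arm M, the same formula gives

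bias = (k_A/n_A) × D_A − (k_M/n_M) × D_M

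The active interventions have two sessions that can be missed, and the minimal one is a message, so k_A could exceed k_M. But the documents give none of k_A, k_M, D_A or D_M, and families can move through several interventions. The sign is not determined.

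**5. What the planned models do.** Table 2 schedules uploads at baseline and every two weeks to week 12. A child withdrawn after week 8 still contributes the uploads up to then. A likelihood-based growth model can use them, and it removes the bias if missingness depends only on observed data. The plan does not state that assumption, and a discretionary decision by the site need not satisfy it.

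**The case against.** The strongest reply is that the design answers low Auto Mode use with treatment, not removal. An adherence failure leads to randomisation, repeat failures are provided for, and the last of the numbered checkpoint rules ends in no treatment, not in withdrawal. A family with low use that uploads and takes its calls is following the protocol. This stands. A reader might infer that low Auto Mode use is itself a ground for withdrawal, but no text says so. The risk comes from the term being undefined.

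A reader might also infer that the worst responders leave the analysis. That is too strong. Data before withdrawal are kept, the planned models work from checkpoint to checkpoint, and no completers-only rule is stated. What can be lost is the later checkpoints and the week-12 value.

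The illustration is open to challenge too. Its 1- and 2-point shifts are below one standard error of the completer mean (15/√27 = 2.9 and 15/√24 = 3.1), and they come from a completers-only mean that the plan does not specify. That is fair as to size. It does not dispose of the point, because a shift smaller than a standard error still passes into the effect sizes that the plan wants for the next trial.

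Finally, this is a pilot that already calls its individual-intervention tests underpowered. That lowers the stakes, but it does not excuse an avoidable loss of data.

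**Conclusion.** The point holds as a possible bias. The protocol allows withdrawal after randomisation for undefined non-compliance and uses data only up to that moment, in a trial where adherence is trigger, objective and outcome. If the rule is used, loss of later checkpoints and of the week-12 time-in-range value can be related to outcome.

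The documents do not give its size. The figure of 1 to 2 points, or 10% to 20% of the 10-point target, is tempting to quote as an estimate. It rests on assumed zero gain in withdrawn families, assumed numbers withdrawn and an assumed completers-only mean. The direction between arms is also open: a reader might infer that active interventions are favoured because they have sessions to miss, but the documents neither make a missed session a ground for withdrawal nor give the quantities that would fix the sign. The growth models may reduce the bias, on an assumption the plan leaves unstated. Amending the rule is a cheap improvement.

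**What to change.** In Subject withdrawal:

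- State that an adherence failure, a glucose failure or a missed session is not by itself a ground for withdrawal from the study.
- Separate stopping of sessions from stopping of follow-up. Families whom the investigator takes off sessions stay in the analysis as randomised. Their 670G uploads continue to week 12, and the week-12 visit takes place if the family agrees.
- Leave the family's own right to withdraw unchanged.

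In Biostatistics and Data Analysis, add that withdrawals will be reported by reason and by assigned intervention, so that readers can judge whether the loss was selective.

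**Cost:** protocol and consent wording, and some follow-up of families who no longer take part in sessions. Uploads are already scheduled at every visit in Table 2, so the added burden is modest. Continuing them must be covered by the consent, whose text is not in the public document.
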